Visit Schedule	
Visit 1 - Screening Study day 0
 
 • Demographic data • Medical history and risk factors • ICF • Randomization • Primary and secondary outcomes 
Visit 2 - Efficacy Evaluation Study day 30
 
 • Primary Outcomes • Secondary Outcome 
Visit 3 - Efficacy Evaluation Study Day 90
 
 • Primary Outcomes • Secondary Outcome

Protocol Number: FSNANO08032022 -2.0 amendment 1 Date: 20032023	
STUDY Code: N-HANCE	Page 7 of 26

	Visit 4 - Efficacy Evaluation Study Day 180
	
 • Primary Outcomes • Secondary Outcome
Active dietary supplementation arms	N-Pep-12 (45 mg), daily (Day 0-Day 180) N-Pep-12 (90 mg), daily (Day 0-Day 180)
Reference Product	Placebo – Lactose (Day 0-Day 90)

*All treatment cycles and efficacy evaluations will be performed within a window of ± 3 working days

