2. INTRODUCTION

2.1 Background Information and Study Rationale

The global older population is growing, particularly in developed countries. The number of people aged 60 and up is expected to reach two billion by 2050, up from 900 million in 2015 (He, Goodkind, & Kowal, 2016). Normal mental performance is a vital aspect of quality of life and wellbeing. With greater longevity and shifting demographics, it is more important than ever to understand the characteristics that enable healthy aging (Simpson et al., 2014) and find solutions that can enhance the cognitive processes and overall mental wellbeing that come with the natural process of aging.

The basic mechanisms involved in attention, perception, memory, and learning are referred to as cognitive functions (Eysenck, 2018). The majority of cross-sectional studies on healthy individuals suggest that attention, working memory, and information processing speed deteriorate gradually between the ages of 20 and 60 (Af, L, Sj, W, & Wt, 2004; Craik & Byrd, 1982; Salthouse, 2009). Moreover, lower cognitive ability and greater decline in cognitive ability predict mortality in older people, even when other biomedical risk factors are controlled for (Batterham, Mackinnon, & Christensen, 2012; Connors, Sachdev, & Kochan, 2015).

N-PEP-12 is a peptide-based nutritional supplement that has been proven in experimental studies and early clinical studies to have neuroprotective and pro-cognitive effects in patients with age-related cognitive impairments (Crook, Ferris, Alvarez, Laredo, & Moessler, 2005; Hutter-Paier, Reininger-Gutmann, Wronski, Doppler, & Moessler, 2015). After only 30 days of a once-daily intervention with 90 mg of N-PEP-12, it was found to considerably improve memory impairment in older persons with subjective memory complaints (Crook et al., 2005). Memoprove and Cebrium are two brands of the chemical that are available in film-coated pills or capsules.

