3.1 Primary Objectives

To assess the efficacy of N-PEP-12 on the Test of Attentional Performance outcomes in healthy middle-aged and older adults at 90 days after baseline.

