3.2 Secondary Objectives

To assess the efficacy of N-PEP-12 on individual outcomes (cognitive function, functional outcome, mental wellbeing, mood, and quality of life) in healthy middle-aged adults at 30, 90 and 180 days after baseline.

To assess the efficacy of N-PEP-12 on the Test of Attentional Performance outcomes in healthy middle-aged and older adults at 30 and 180 days after baseline.

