4. STUDY DESIGN

Randomized, placebo-controlled, double-blind

N-PEP-12 groups shall be tested against Placebo. The 3 groups are:

Study Group 1: 45mg N-PEP-12

Study Group 2: 90mg N-PEP-12

Study Group 3: Placebo (Lactose)

The trial will be conducted in a sample of healthy middle-aged and older adults, with subjective cognitive function complaints. The study extends over an observation period of 180 days. Four visits for clinical evaluation are planned as follows:

Visit 1 - (Study day 0) - Screening - will consist of the baseline assessment - demographic data and the patient's medical history and risk factors will be collected. Also, the informed consent will be signed and the patient will be randomized. **Visit 2 - (Study day 30)** will be an efficacy evaluation. Between Visit 1, Visit 2 and **Visit 3 - (Study day 90)** patients shall receive their treatment, based on the group they have been allocated at baseline: Placebo, 45mg N-PEP-12 or 90 mg N-PEP-12. Between Visit 3 and **Visit 4 - (Study day 180)** the patients shall continue the treatment with the two N-PEP-12 groups unchanged and the initial Placebo group receiving 90 mg N-PEP-12.

All treatment cycles and efficacy evaluations will be performed within a window of ± 3 working days.

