12. STATISTICAL METHODS

The final statistical analysis of the study will be performed by a qualified biometrician and will fulfill all ICH/GCP requirements for handling clinical study data. The statistical analysis, including any subgroup analysis will be agreed upon prior to data evaluation and the results will be fixed in a statistical analysis plan (SAP) which will be established prior to unblinding of the data. The study data will be analyzed and

Protocol Number: FSNANO08032022 -2.0 amendment 1 Date: 20032023	
STUDY Code: N-HANCE	Page 18 of 26

the Statistical Report written as soon as all study data are entered into the study database and the entered data are validated.

The analysis will be based on pre-specification of the primary analyses and control of multiple level alpha. The power for this study is determined based on the following design specifications:

- K=2 experimental treatments will be included in the trial.
- A significance level of $\alpha=0.05$ will be used, in combination with Dunnett's correction.
- The standard deviations of the responses will be assumed to be: $(\sigma_0, \dots, \sigma_K)=(1, 1, 1)$.
- The minimum marginal power will be controlled to level $1-\beta=0.9$ under each of their respective least favourable configurations.
- The interesting and uninteresting treatment effects will be: $\delta_1=0.5$ and $\delta_0=0$ respectively.
- The target allocation to each of the experimental arms will be: the same as the control arm.
- Therefore, the realised allocation ratios to the experimental arms are: $(r_1, \dots, r_K)=(1, 1)$.
- The maximum familywise error-rate is: 0.05.
- The minimum marginal power is: 0.9.
- The following critical threshold should be used with the chosen multiple comparison correction: 0.028.
- 10% adjustment for dropouts
- The total required sample size is: $N=270$. The required sample size in each arm is: $(n_0, \dots, n_K)=(90, 90, 90)$.

Source: Grayling MJ, Wason JMS (2020) A web application for the design of multi-arm clinical trials. *BMC Cancer* 20:80. DOI: 10.1186/s12885-020-6525-0

It is the primary endpoint of this study to assess the efficacy of N-PEP-12 on the Test of Attentional Performance outcomes in healthy middle-aged and older adults at 90 and 180 days after baseline.

Missing data

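### Section 12 adds Day 180 to the primary endpoint, which contradicts the synopsis and objectives and names a time point at which no arm is on placebo

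*Protocol*

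**What the plan says.** The protocol gives the time point of the primary TAP assessment in several places, and they do not agree.

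- Section 12 (Statistical Methods): the primary endpoint is "efficacy of N-PEP-12 on the Test of Attentional Performance outcomes in healthy middle-aged and older adults at 90 and 180 days after baseline".
- Section 3.1 (Primary Objectives): TAP "outcomes in healthy middle-aged and older adults at 90 days after baseline". The synopsis sets the same single time point.
- Section 3.2 (Secondary Objectives): TAP "outcomes in healthy middle-aged and older adults at 30 and 180 days after baseline". The synopsis again agrees.

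On treatment after Day 90, section 4 (Study Design) says that "the patients shall continue the treatment with the two N-PEP-12 groups unchanged and the initial Placebo group receiving 90 mg N-PEP-12". The synopsis lists the reference product as "Lactose (Day 0-Day 90") and both active arms as running to Day 180. Section 4 also says that the N-PEP-12 groups are to be tested against placebo.

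The sample-size text in section 12 assumes two experimental arms, a 0.5 SD difference from control, SD 1, Dunnett's correction at familywise 0.05, marginal power 0.9, a critical threshold of 0.028 and a 10% dropout adjustment. The result is 90 per arm, 270 in total. It makes no provision for a second primary time point.

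**The concern.** The same measurement, TAP at Day 180, is primary in section 12 and secondary in the synopsis and section 3.2. That leaves room to choose the primary time point later, although section 12 itself promises that the primary analyses will be pre-specified.

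Day 180 also differs in kind from Day 90. By then every arm is on N-PEP-12, so no Day-180 contrast between arms can show efficacy against placebo, which is what the design and the power calculation are about.

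Section 12 does not say how two primary times would be combined. If either suffices, more tests share a threshold set for two. If both are required, success depends on a Day-180 difference for which the protocol gives no value.

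**Working it through.** **1. What each contrast compares** (sections 1 and 4)

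| Arm | To Day 90 | Day 90 to 180 |
|---|---|---|
| Group 1 | 45 mg | 45 mg |
| Group 2 | 90 mg | 90 mg |
| Group 3 | placebo | 90 mg |

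At Day 90, groups 1 and 2 are each compared with placebo. At Day 180, group 2 versus group 3 is 180 days of 90 mg against 90 days of 90 mg (early versus delayed start). Group 1 versus group 3 is 180 days of 45 mg against 90 days of 90 mg.

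**2. Reproducing the stated sample size for one time point**

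Section 12 does not state sidedness, so both forms were tried. With two contrasts sharing a control at 1:1:1, their correlation is 0.5.

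- One-sided Dunnett at familywise 0.05: critical z = 1.916, p = 0.0277, which rounds to the stated 0.028.
- n per arm = 2(z + 1.282)²/0.5² = 2(1.916 + 1.282)²/0.25 = 81.8, so 82.
- Dropout: 82 × 1.10 = 90.2, and 246 × 1.10 = 270.6. These match 90 and 270.
- Two-sided Dunnett (z = 2.212) gives 98 per arm, or 108 to 109 after dropout, and does not match.

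So the stated figures are those of two one-sided active-versus-control comparisons of one response at one time. They are used as such below.

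**3. If success at either time counts**

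There are four tests (two arms, two times), each at z = 1.916, with no true difference anywhere. The between-time correlation is not in the protocol and is assumed. Simulation (2,000,000 draws per row) gives:

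| Between-time correlation | Familywise error |
|---|---|
| 0 | 9.7% |
| 0.5 | 8.9% |
| 0.7 | 8.2% |
| 0.9 | 6.9% |

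Check at correlation 0: 1 − 0.95² = 0.0975.

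**4. If both times must succeed**

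The rejection rate at Day 180 is Φ(d·√(n/2) − 1.916), where d is the remaining difference in SD units. The values of d are assumptions. Evaluable n is 82 (the design figure) or 81 (90 × 0.9).

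| d at Day 180 | n = 81 | n = 82 |
|---|---|---|
| 0.5 | 0.897 | 0.901 |
| 0.25 | 0.372 | 0.376 |
| 0 | 0.028 | 0.028 |

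The last row is the false-positive rate, not power.

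Joint success for the 90 mg arm was simulated with a true Day-90 difference of 0.5 SD, n = 82 and between-time correlation 0 to 0.9. It is 81% to 87% if the full 0.5 SD remains at Day 180, 34% to 38% at 0.25 SD, and 2.5% to 2.8% at no difference. Even the first of these is below the stated 90%.

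**The case against.** The strongest reply is that the section 12 sentence is a drafting slip. The synopsis and section 3 consistently make Day 90 primary and Day 180 secondary, and the design then makes sense: placebo-controlled to Day 90, followed by an extension in which the placebo arm is switched. This is probably the right reading, and it means that the design itself is not at fault. It does not remove the point, because the protocol states no order of precedence and the sentence stands in the section that governs the analysis. Nor can an unseen SAP settle it while the protocol states two incompatible primary endpoints.

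The other side is right to limit four further inferences that a reader might draw.

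- *The synopsis contradicts section 4.* It does not. It ends placebo at Day 90 and is silent on what follows, and section 4 fills the gap.
- *The effect must shrink or vanish by Day 180.* Section 2.1 reports of the product that "After only 30 days of a once-daily intervention with 90 mg of N-PEP-12, it was found to considerably improve memory impairment". That concerns memory, not TAP. It makes catch-up possible but does not establish it, and it gives no basis for predicting which way 45 mg versus delayed 90 mg would fall.
- *The low power figures describe this trial.* They rest on assumed residual differences that appear nowhere in the protocol.
- *Day 180 may only be described.* Early versus delayed start is a randomised contrast and can be formally tested if it is labelled correctly. Uncontrolled change within arms would not be an improvement.

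**Conclusion.** The point holds as an inconsistency about the primary endpoint. Section 12 conflicts with the synopsis and sections 3.1 and 3.2, and the time point that it adds cannot measure efficacy against placebo under section 4. This follows from the text and needs no assumption.

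The numerical consequences are conditional. The sample size and threshold reproduce for one time point, on the one-sided reading that the stated 0.028 and 90 per arm imply. An either-time rule would raise familywise error from 5% to between about 6.9% and 9.7%, depending on the assumed between-time correlation. A both-times rule would leave power resting on a Day-180 difference that the protocol does not state.

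A reader might go further and conclude that half of the primary evidence is invalid, or that the trial is underpowered. The documents do not support that: with Day 90 as the only primary time point, the placebo comparison is intact and 90 per arm reproduces.

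**What to change.** - In section 12, delete the words *and 180* from the primary-endpoint sentence, so that TAP at Day 90 is the sole primary time point throughout.
- Keep Day 180, for TAP and the other scales, as secondary. State in sections 3.2 and 12 that its between-arm contrast is early versus delayed start of 90 mg, and 45 mg versus delayed 90 mg, with no claim of efficacy against placebo.
- Leave to the SAP whether the Day-180 contrast is formally tested or only described.
- Optionally, add the section 4 switch to the synopsis for clarity.

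The cost is wording in a protocol amendment. No participants, visits or changes to the treatment schedule are involved. What is given up is a Day-180 claim against placebo that the design cannot support.

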5.2 Patient Exclusion Criteria

- History of drug abuse or alcohol abuse (drank more than 14 units/week of alcohol: 1 unit =285ml beer, 25ml spirits or 100ml Wine)
- Gastric sleeve patients
- History of drug abuse within 5 years prior to screening, or urine drug screening test was positive
- Other clinically major diseases, such as decompensated, in the investigator's judgement (such as neuropsychiatric system, cardiovascular system, urinary system, digestive system, respiratory system, metabolic endocrine system, blood system, skin diseases, immune diseases, tumors, etc.)
- Participation in another clinical trial within 3 months prior to enrollment
- Pre-existing and active major neurological disease
- Injury of writing hand influencing cognitive or other outcome measures, in the investigator's judgment.

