8.1.1.1 Alertness Subtest

For the Alertness (phasic alertness) subtest, the reaction time is tested under two conditions. The first

Protocol Number: FSNANO08032022 -2.0 amendment 1 Date: 20032023	
STUDY Code: N-HANCE	Page 12 of 26

condition involves simple reaction time measurements in which a cross appears on the monitor at irregular points and the subject must respond as quickly as possible by pressing a key (Zimmerman & Fimm, 2022).

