Missing data of the type 'missing completely at random' (MCAR), which in principle will not bias the results; the analysis procedure should be able to cope with partially missing data of such a type. In many studies this type of data is treated by LOCF replacement (Last Observation Carried Forward) as far as there exist follow-up measurements at previous visits.

In a study like the one planned there might also be informatively missing data (missing not at random, MNAR): participants of the study died or are unable to complete the tests because of brain-related impairment. Neglecting these missing data might introduce bias.

In order to identify each type of missing data, outcome scales will be coded for every patient and visit according to the following scheme:

- 1 = valid (complete task)
- 2 = unable to complete (TBI-related neurological reason) [describe reason]
- 3 = not completed (different reasons, not TBI related) [describe reason].

For outcome scales with code "2" a worst rank imputation will be introduced for the corresponding patients since these data are informatively missing (missing not at random, MNAR). These missing data are replaced by the worst possible score of the corresponding outcome scale.

For outcome scales with code "3" a LPCF replacement will be introduced (Last Percentile Carried Forward) as far as previous follow-up evaluations exist. This method carries forward the actual status information of

Protocol Number: FSNANO08032022 -2.0 amendment 1 Date: 20032023	
STUDY Code: N-HANCE	Page 19 of 26

the patient population, using the percentile value with back transformation to raw scale, instead of the last value carried forward. This approach was recently developed and recommended by O’Brien, Zhang and Bailey (2005) for the analysis of data from chronic, progressive diseases such as dementia. According to their simulation study the calculated estimators should be negligibly biased by missing data. If no general change of patients over time occurs the method is more or less identical with LOCF (Last Value Carried Forward), if change occurs bias is minimized. If no previous follow-up measurement exists, the outcome scale remains missing.

Study populations and protocol violations

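### The code for informatively missing outcomes is limited to TBI, so deaths and impairments the plan calls MNAR are carried forward; read more widely, its worst score is undefined for TAP

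*Protocol*

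**What the plan says.** Section 12 of the protocol (Missing data) gives as examples of informatively missing data that "participants of the study died or are unable to complete the tests because of brain-related impairment", and warns that neglecting such data might bias the results. It then codes every outcome scale for each patient and visit:

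- Code 1 is a valid, completed task.
- Code 2 is "2 = unable to complete (TBI-related neurological reason) [describe reason".
- Code 3 is "3 = not completed (different reasons, not TBI related) [describe reason".

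For code 2, "a worst rank imputation will be introduced for the corresponding patients since these data are informatively missing", and the next sentence gives the rule: "These missing data are replaced by the worst possible score of the corresponding outcome scale". For code 3, "a LPCF replacement will be introduced (Last Percentile Carried Forward) as far as previous follow-up evaluations exist"; without an earlier follow-up the value stays missing.

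Sections 4 and 5.1 describe the sample as healthy adults aged 50 to 75 with subjective complaints and MoCA above 25. Section 5.2 excludes "Pre-existing and active major neurological disease". TBI is mentioned nowhere in the protocol except in these two codes. For the Alertness subtest, Section 8.1.1.1 says "the reaction time is tested under two conditions" and gives no upper limit. Sections 8.1.1.2 and 8.1.1.3 describe the Working Memory and Divided Attention tasks but not the parameter that is scored.

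**The concern.** The codes do not implement the rationale stated just before them. The rationale covers death and any brain-related impairment; code 2 covers only TBI. A participant who dies, has a stroke or becomes cognitively unable to do the test belongs to the group that the plan calls MNAR, yet falls literally under code 3. That participant is then credited at Day 90 with the Day 30 percentile, or left missing if there was no Day 30 test.

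Reading code 2 more widely, as any neurological reason, raises a second problem. The rule then inserts a worst possible score into TAP outcomes for which the protocol defines none. In a comparison of means, that arbitrary number affects both the difference and its standard deviation.

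The two consequences are alternatives, depending on how code 2 is read. They do not add up.

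**Working it through.** **The plan's own figure.** Inputs from Section 12: two active arms, Dunnett, familywise error 0.05, threshold 0.028, effect 0.5, SD 1, power 0.9, 10% dropout, 90 per arm. With correlation 0.5 between the two comparisons, the one-sided Dunnett critical value is 1.916 (p threshold 0.0277).

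n = 2 × ((1.916 + 1.282) / 0.5)² = 81.8, so 82 per arm. With the uplift, 82 × 1.1 × 3 = 270.6, against the stated 270. The design reproduces as one-sided; a two-sided version needs 98 per arm before dropout. After 10% dropout, 90 × 0.9 = 81 per arm remain.

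**Which code applies**

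| Reason the test is missing | Stated rationale | Code as written | Handling |
|---|---|---|---|
| Death not related to TBI | MNAR | 3 | LPCF |
| Stroke or new cognitive failure | MNAR | 3 | LPCF |
| Head injury during the trial | MNAR | 2 | worst score |
| Other reasons, e.g. administrative | not named as MNAR | 3 | LPCF |

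Only the third row reaches the MNAR rule.

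**Size under the literal reading.** Assumption: a participant given LPCF would truly have been 2 SD worse. One such participant shifts an arm mean by 2/81 = 0.025 SD. An imbalance of two between arms shifts the difference by 2 × 2/81 = 0.049 SD, about a tenth of the planned 0.5. Equal numbers in the arms largely cancel.

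**Size under the wider reading, if means are compared.** Assumptions: m participants per arm of 81 are set k SD away from the mean, with k = 5 or 10; the protocol gives neither. With p = m/81 and the difference held at 0.5:

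SD = √(1 + p(1 − p)k²); power = Φ(0.5 × √(81/2) / SD − 1.916) = Φ(3.182/SD − 1.916)

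| m per arm | k | SD | Power |
|---|---|---|---|
| 0 | – | 1.00 | 0.90 |
| 1 | 5 | 1.14 | 0.81 |
| 1 | 10 | 1.49 | 0.59 |
| 2 | 5 | 1.27 | 0.72 |
| 2 | 10 | 1.85 | 0.42 |

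An imbalance of two shifts the mean difference by 2/81 × 5 = 0.12 SD or 2/81 × 10 = 0.25 SD.

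**Means against ranks.** This check uses 90 per arm, with 2% of each arm set 3, 5 or 10 SD below the control mean, and lets the difference shrink accordingly. Power for means falls from about 0.925 to 0.86, 0.77 and 0.49. In 20,000 simulated trials a rank test had power of about 0.91 with none imputed, and at 2% imputed about 0.88 to 0.89 at all three values.

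**The case against.** The strongest reply is that little is likely to happen in practice. Few deaths or neurological failures are expected in healthy adults over 90 days, both codes ask for the reason in free text, and Section 12 provides for a blind review before unblinding. All of this stands, and it lowers the severity. It does not remove the contradiction, and a later SAP does not cure it either, because the protocol itself fixes the codes and the imputation for each.

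Several stronger conclusions might be drawn, but the documents do not support them:

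- **Power is lost as the plan stands.** The power figures need a wide reading of code 2, a comparison of means and an extreme imputed value. SD-based Dunnett sizing suggests means, but the protocol does not fix the test, and it does use the term worst rank.
- **No TAP outcome has a worst score.** Only Alertness is described as a reaction time. The other two subtests could be scored as bounded counts, and normed scores might be bounded too. For those two, undefined is the most that can be said.
- **The text was copied from a brain-injury trial.** This is plausible, since Section 10.2 also counts IV infusions in an oral supplement study, but it remains an inference.
- **Nobody with TBI can enter.** Section 5.2 excludes pre-existing and active major disease; past TBI is not expressly excluded.
- **Leaving code 3 missing without a Day 30 test is a separate error.** The ITT definition already requires a post-baseline observation of a primary criterion. What remains is mainly participants who return only at Day 180 or lack a single subtest.

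**Conclusion.** The point holds in limited form. The missing-data rule is wrong as written: the MNAR code excludes almost every case that the same section calls MNAR, and those cases receive carry-forward instead. The likely effect on the Day 90 comparison is small, about 0.05 SD for an imbalance of two participants per 81, assuming a true value 2 SD worse.

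The larger figures, power of 0.81 or 0.59 with one imputed participant per arm, hold only if code 2 is read widely, means are compared and the worst value lies 5 or 10 SD out. They show that the worst value cannot be left open under a mean-based analysis; they do not forecast the trial's power. The sample size of 270 is unaffected. This should be fixed before unblinding, but it does not by itself undermine the trial.

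**What to change.** In Section 12:

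1. Delete TBI from both codes. Define code 2 as died, or unable to complete because of any new neurological or cognitive impairment, and code 3 as all other reasons.
2. Recode existing records under blind from the recorded reasons, before unblinding.
3. For code 2, either analyse by ranks, so that worst rank means what it says, or pre-specify a finite worst value for each scored TAP parameter. Add a sensitivity analysis of that choice.

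The cost is a few sentences in the protocol, a relabelled CRF field, a blinded pass through the recorded reasons and one extra analysis.

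Replacing LPCF with a repeated-measures likelihood model, or adding a tipping-point analysis, is optional and not needed to correct this error. Such a model as the primary analysis assumes missing at random, and so would itself treat deaths and neurological inability as ignorable.

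### Last-percentile imputation crosses the placebo arm's Day 90 switch to N-PEP-12 without an exception, and can overstate the Day 180 difference in favour of the original N-PEP-12 arms if the product works

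*Protocol*

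**What the plan says.** Section 12 (Missing data) sets the imputation by reason code: "outcome scales will be coded for every patient and visit". For code 3, not completed for other reasons, "a LPCF replacement will be introduced (Last Percentile Carried Forward) as far as previous follow-up evaluations exist". The percentile is described as carrying forward the status of "the patient population, using the percentile value with back transformation to raw scale, instead of the last value carried forward". The text does not say whether ranking is over all arms or within arm.

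Two limits are stated. First, "If no previous follow-up measurement exists, the outcome scale remains missing". Second, code 2 gaps are handled differently: "These missing data are replaced by the worst possible score of the corresponding outcome scale".

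Section 4 describes the treatment after Visit 3. The two N-PEP-12 arms continue unchanged, with "the initial Placebo group receiving 90 mg N-PEP-12". The synopsis agrees, ending the lactose period at Day 90.

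Day 180 matters to the stated aims. Section 3.2 lists TAP "outcomes in healthy middle-aged and older adults at 30 and 180 days after baseline" as a secondary objective and includes Day 180 for the other secondary outcomes. Section 12 goes further and names Day 180 beside Day 90 in the primary endpoint, which conflicts with sections 3.1 and 3.2.

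**The concern.** Last-percentile imputation assumes that a participant's rank relative to the others persists between visits. Section 12 defends it on the ground that it follows change in the population over time. That defence covers change shared by everyone. The planned switch changes treatment in one arm only, between the last two visits, so if the product works, relative standing is not expected to persist.

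A placebo-start participant with a code-3 gap at Day 180 receives a percentile from Day 90 (or Day 30 if Day 90 is also missing), measured on lactose and possibly ranked against arms already taking N-PEP-12. It is entered as a Day 180 score for an arm then assigned 90 mg. The original N-PEP-12 arms get the opposite error, because their Day 90 ranks were raised by comparison with placebo.

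After the switch, a Day 180 comparison by randomised arm contrasts early start with late start. The imputation can leave a difference where late starters have in fact caught up, and a reader could take it for a lasting benefit of starting earlier.

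**Working it through.** **Planning figures reproduced first.** Section 12 gives two experimental arms, Dunnett correction at 0.05, effect 0.5, SD 1, power 0.9, threshold 0.028, 10% dropout and 90 per arm. The one-sided Dunnett critical value for two comparisons with correlation 0.5 is 1.916, a p-value threshold of 0.0277, which rounds to 0.028. Then n = 2 × ((1.916 + 1.282) / 0.5)² = 81.8 per arm, and 81.8 × 1.1 = 90. The two-sided version has critical value 2.212, threshold 0.0270 and 98 per arm before dropout, so it does not match. The protocol does not state sidedness, so both are shown below.

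**Inputs for the bias.** From section 12: δ = 0.5 SD at Day 90, SD 1, 90 per arm and 10% as the central missing share. Assumed here: Day 90 observed, code-3 gaps at random and equal across arms, higher score better, both N-PEP-12 arms with the same effect, percentiles ranked over all arms. Let m be the share missing at Day 180 and f the fraction of the effect that the placebo-start arm has gained by then.

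**Step 1, pooled distribution at Day 90.** Means are 0, 0.5 and 0.5. The pooled mean is 0.333 and the pooled SD is √(1 + 0.5² × 2/9) = 1.027. The average standing is (0 − 0.333)/1.027 = −0.32 for placebo start and (0.5 − 0.333)/1.027 = +0.16 for the N-PEP-12 arms.

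**Step 2, mapping to Day 180.** The difference among imputed scores is about δ × (pooled SD at Day 180) / 1.027. The true difference is δ(1 − f). The bias is m times the gap between them, roughly m × δ × f.

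- Full catch-up (f = 1, pooled SD 1): 0.5/1.027 = 0.487, true difference 0. Bias = 0.10 × 0.487 = 0.049 SD, or 0.097 SD at m = 20%.
- Half catch-up (pooled SD √(1 + 0.25² × 2/9) = 1.007): 0.5 × 1.007/1.027 = 0.490, true difference 0.25. Bias = 0.10 × 0.240 = 0.024 SD.
- No catch-up (pooled SD unchanged): 0.5 − 0.5 = 0.
- No drug effect: 0.

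**Step 3, error rate with full catch-up.** The standard error of the contrast is √(2/90) = 0.149.

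- m = 10%: shift 0.049/0.149 = 0.33. One-sided P(Z > 1.916 − 0.33) = 0.056. Two-sided P(Z > 2.212 − 0.33) + P(Z < −2.212 − 0.33) = 0.030 + 0.006 = 0.035.
- m = 20%: shift 0.65. One-sided 0.103, two-sided 0.062.

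**Step 4, simulation of the rule.** Independent simulations used 90 per arm and a Day 90 to Day 180 correlation of 0.7. Ranges show the spread between runs.

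| Setting (original 90 mg arm minus placebo start) | Bias, 10% missing | Bias, 20% missing |
|---|---|---|
| Pooled ranks, 0.5 SD, full catch-up | 0.046 to 0.050 | 0.094 to 0.095 |
| Pooled ranks, 0.5 SD, half catch-up | 0.023 to 0.024 | 0.043 |
| Pooled ranks, 0.5 SD, no catch-up | −0.001 | −0.004 |
| Pooled ranks, no drug effect | 0.000 to 0.003 | 0.000 |
| Pooled ranks, effect −0.5 SD, full catch-up | −0.048 | −0.094 |
| Within-arm ranks, 0.5 SD, full catch-up | −0.002 to −0.001 | −0.002 to 0.001 |

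In the first row at 10% missing, rejection was 0.057 to 0.061 one-sided and 0.035 to 0.037 two-sided. Changing the correlation to 0.5 or 0.9 gave 0.050 and 0.058 one-sided. A 0.3 SD effect with full catch-up and 10% missing gave a bias of about 0.03 SD and one-sided rejection of 0.043 to 0.046.

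**The case against.** **Second-order size.** A bias of 0.05 SD is a tenth of the design effect and about a third of the contrast's standard error (0.049/0.149). If the tests are two-sided, the rise in rejection at 10% missing is under one percentage point. The absence of a concurrent placebo after Day 90, and the conflict over whether Day 180 is primary, weigh more on Day 180. This stands, and it limits the weight of the point.

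**Unstated ranking set.** The protocol does not say that ranks are pooled, and such a detail could be settled in a statistical analysis plan. That is fair. Pooling is the natural reading of a phrase about the patient population, but the bias depends on it. The carry-over across the switch does not: that rule is stated and has no exception.

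**Generous missing share.** The 10% is dropout for the whole study, whereas the calculation places it all after an observed Day 90. A placebo participant who left before taking any 90 mg may be described fairly by lactose-period data, depending on the estimand, which the protocol does not give. This also stands, but the rule covers every code-3 gap, not only those participants.

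**Stronger readings.** A reader might infer that the rule acts at every visit, always creates an advantage for the N-PEP-12 arms, or could make an inactive product look active. The document does not support these. Day 30 has no earlier follow-up and stays missing, and code 2 gaps get the worst score. The bias is nil without a drug effect and reverses sign if the effect is negative.

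**Conclusion.** The point holds in conditional form. As written, the rule enters a lactose-period standing as a Day 180 score for an arm then assigned 90 mg N-PEP-12. It distorts the Day 180 contrast only if three things are true together: a real Day 90 effect, at least partial catch-up after the switch, and ranking over all arms. Given these, the distortion is modest at the planned dropout and grows roughly in proportion to the share missing, the effect size and the degree of catch-up. It exaggerates a delayed-start difference and leaves the Day 90 comparison untouched by the switch.

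The size rests on the 0.5 SD planning effect, gaps at random and equal across arms, and an observed Day 90. Sidedness and the ranking set are not stated in the protocol. The rule should be changed because Day 180 is a stated objective and the repair is wording only.

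**What to change.** In section 12, state that no value or percentile obtained before the switch at Visit 3 is carried forward to Day 180, in any arm. Leave code-3 Day 180 scores missing, and estimate Day 180 from a mixed model for repeated measures on all observed visits with arm-by-visit terms. This assumes that gaps are at random given the observed data, and it does not borrow ranks across arms. The code 2 rule is untouched, but the analysis plan should say how those worst scores enter the model.

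If last-percentile imputation is kept as a Day 180 sensitivity analysis, state that ranking is within arm. Re-ranking alone is a weaker repair: it removes the bias, but as a single imputation it still understates variance (simulated one-sided rejection 0.032 at 10% and 0.038 at 20% missing, against 0.026 with complete data).

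The cost is wording only, with no change to visits, treatment or sample size. Apparent precision at Day 180 falls slightly. With 10% missing, observed scores alone give a standard error of √(2/81) = 0.157 instead of 0.149, and the model recovers part of that through the earlier visits.
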